## 2.4 Overview of Sample Size Considerations

We plan to enroll a total of 185 participants; approximately 110 in Arm 1, 55 in Arm 2, and 20 in Arm C. We estimate that we will have at least 90% power to detect an effect between Arm 1 and Arm 2 with respect to the primary efficacy outcome. We assume 70% culture conversion by week 12 in Arm 2 and a hazard ratio of 1.8. We use a 2:1 allocation ratio and assume that 10% of participants will have unevaluable culture conversion results.

For the primary safety outcome, we will compare proportions of participants with any Grade 3 or higher adverse events (AE) between Arms. Table 10.4-2 from the study protocol (copied below) gives the power we would have to detect that Arm 1 is inferior to Arm 2 assuming a two-sided type 1 error of 0.10, 10% probability of developing an AE in the SOC Arm, and varying probabilities (15-30%) of developing an AE in experimental Arm. We also provide the 90% confidence interval (CI) width for the comparison.

Protocol Table 10.4-2

Power	N1	N2	N	Arm 1 Proportion with $\ge$ Grade 3 AE	Arm 2 Proportion with $\ge$ Grade 3 AE	Two-sided type 1 error	90% CI Width
0.13	100	50	150	0.15	0.10	0.10	0.210
0.36	100	50	150	0.20	0.10	0.10	0.218
0.64	100	50	150	0.25	0.10	0.10	0.225
0.85	100	50	150	0.30	0.10	0.10	0.230

## 2.5 Overview of Formal Interim Monitoring

The Data and Safety Monitoring Board (DSMB) will perform an initial review of the study between 4-6 months after the first enrollment, and thereafter at least every 6 months or on another schedule requested by the DSMB. For all reviews, we will provide the DSMB with detailed information on safety, tolerability, and administrative aspects (including accrual, retention, and compliance with study requirements).

There was one planned interim analysis for futility of the primary efficacy outcome using a conditional power approach. This analysis was to be conducted once 50% of participants had reached week 12 of follow-up. However, due to the early close to accrual, this interim analysis will not be completed.

### 3 Outcome Measures

#### 3.1 Primary Outcome Measures

##### 3.1.1 Early Efficacy

Time to stable culture conversion in liquid media, defined as the first of two (consecutive or non-consecutive) negative sputum cultures without an intervening positive culture, and/or visits wherein the participant is unable to produce sputum and has no signs of active TB, up to 12 weeks post-randomization.

##### 3.1.2 Safety

Proportion across study arms experiencing any Grade 3 or higher AE that is at least a one-grade increase from baseline over 65 weeks

#### 3.2 Secondary Outcome Measures

##### 3.2.1 Composite Efficacy

A: Proportion with favorable clinical/bacteriologic outcome at 65 weeks post randomization

B: Proportion with favorable composite outcome including treatment completion at 65 weeks post-randomization.

Favorable, unfavorable, and unevaluable clinical/bacteriological outcomes (A) are defined as follows:

##### Favorable Outcome (any one of the following scenarios)

- Participants with liquid culture negative status at week 65.
- Participants without signs or symptoms of ongoing active TB and are unable to produce a sputum specimen at 65 weeks.
- Participants who at the end of the follow-up period are clinically without symptoms/signs of ongoing active TB and produce a sputum specimen that is contaminated in two liquid cultures without evidence of TB.

For any of the above to be considered favorable, participants must not already have been considered unfavorable, as defined below.

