The following are changes (noted in bold or strikethrough) to A5362, Version 2.0, 08Jul2022, titled A “Phase IIc Trial of Clofazimine- and Rifapentine-Containing Treatment Shortening Regimens in Drug-Susceptible Tuberculosis: The CLO-FAST Study.” These changes will be included in the next version of the A5362 protocol if it is amended at a future date. Changes that have already been made (Clarification Memo #1) have been incorporated in the excerpted text shown below (and are no longer presented in bold or strikethrough).

1. Section SCHEMA, DESIGN

The following information has been added to reference the change in study design due to a DSMB review.

Per the June 1, 2023 DSMB review, and permanent closure of accrual, the follow-up schedules for Arm 1 participants will be revised as follows:

- Participants currently on Arm 1 study treatment should complete the 3-month regimen and then be placed on an additional 3 months of continuation phase rifampicin/isoniazid (RH). Based on the DSMB recommendations, an additional 3 months of treatment is necessary to decrease the likelihood of treatment failure and TB relapse in study participants.
- Participants who have already completed Arm 1 treatment should be seen for a follow-up visit within the next 4 weeks of the date of this LOA, at a scheduled or unscheduled visit, to assess whether further treatment is needed.
- Additional extended follow-up visits for participants in Arm 1 will be added at weeks 30, 38, 60, 91 and 117 unless the participant has already been referred for, or already received, 6 months of SOC through the local TB program. The additional visits at weeks 30, 38, and 60 may be performed by telephone only; these calls are to assess the participant’s TB symptoms and determine if it is clinically indicated that the participant should come in for an in-person visit to assess the need for possible poor treatment response (PPTR) assessments and/or referral to SOC treatment.
- If the site investigator diagnoses TB recurrence at any time during Arm 1 follow up, the participant should be referred to 6 months of SOC treatment by the national TB program. For study purposes, such participants should continue to be followed in the study for outcome determination, unless the participant withdraws consent.

Participants in Arm 2 and Arm C should complete their treatment and follow-up schedule as planned; no additional visits are planned for these groups.

2. Section SCHEMA, DURATION

Arm 1:

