6.3.18 TB Symptom Assessment

At weeks 30, 38, and 60, participants in Arm 1, who have not already been referred for 6 months of SOC, will have telephone follow-up visits to assess participants' TB symptoms and determine if it is clinically indicated that the participant should come in for an in-person visit and further TB treatment. If the participant has symptoms concerning for TB in the opinion of the site investigator, an unscheduled in-person visit should be conducted within 1 week to determine if PPTR reporting and evaluations are appropriate, and whether the participant should be referred to the local TB program for 6 months of SOC treatment.

9. Section 10.5.1, Interim Monitoring Guidelines

The first and last sentences have been updated as follows:

Unfavorable Composite Outcome Monitoring in Arm 1

Monitoring for unfavorable composite **clinical efficacy** outcome (per definition 10.2.4A) will begin approximately 1 month after the first participant completes treatment in Arm 1 and will continue approximately monthly and for each DSMB review until the end of the study. Two-sided 95% confidence bands for the cumulative probability of unfavorable outcome over time will be generated. If the lower confidence band for the cumulative probability exceeds 12% at any time, this will trigger a DSMB review. **At all DSMB reviews, the DSMB will also be provided with the cumulative probability of unfavorable composite outcome (and corresponding two-sided 95% confidence interval) according to definition 10.2.4B.**

10. Section 10.5.2, Interim Analysis Plan

The first and third sentences have been revised to read:

Confidence Bands for Unfavorable Composite Outcome Probabilities

Monitoring of the unfavorable composite outcome will be according to definition 10.2.4A. only include treatment failures, treatment extensions, loss to follow-up while culture positive, recurrences, and deaths. Two-sided 95% confidence bands will be

generated for the cumulative unfavorable composite outcome probability in Arm 1. Since Arm 2 data will be lagging 3 months behind Arm 1, the **data** will be presented alongside historical unfavorable proportions for SOC on the REMox, OFLOTUB, and RIFAQUIN trials, and A5362 SOC data as it becomes available. There will be no adjustment to the confidence bands for multiple looks.

11. Appendix I-C, ADDENDUM TO SAMPLE INFORMED CONSENT

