##### Unfavorable Outcome

- Absence of cure. A participant will be considered to have absence of bacteriological cure if a sputum sample obtained at or after end of treatment for Arm 1 (week 13), or at or after week 17 for Arm 2 is culture-positive in liquid or solid media for an *Mtb* strain genotypically matched with the initial isolate. A second sputum sample, obtained at least four hours following the first sputum collection (see section 6.2.3 of protocol), is required to confirm absence of bacteriological cure.
- Participants who die from any cause during study treatment or follow-up except from violent or accidental cause (e.g., road traffic accident).

- Participants who had a positive culture for *Mtb* when last seen, whether confirmed by a second sample or not, unless determined to have been re-infected.
- Participants experiencing extension of treatment beyond the nominal level (week 13 for Arm 1 and week 26 for Arm 2) due to clinically inadequate response. These cases should be managed individually in conjunction with and after having notified the A5362 Clinical Management Committee (CMC). Extension of treatment to make up missed doses will not count as unfavorable.

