#### Unfavorable Outcome

Same as in outcome measure 3.2.1 A, and:

- Participants lost to follow-up during treatment phase of each Arm (i.e., 13 weeks and 26 weeks for Arms 1 and 2, respectively).
- Participants failing to complete treatment (see below for Definitions of Adequate Treatment) and not assessable at the end of the follow-up period.
- Participants receiving any one or more of the following:
  - extension of treatment beyond the nominal level, except to make up missed doses
  - a re-start of treatment following  $\geq 30$  consecutive days lost to follow-up
  - a change in at least one drug in treatment regimen for any reason except re-infection, pregnancy, or temporary drug challenge.

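### The SAP does not say how retreatment for recurrence is scored: composite outcome A as written can count a retreated, bacteriologically unconfirmed recurrence as favorable, and outcome B is unclear

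*SAP*

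**What the plan says.** **Referral and follow-up (LOA #1).** Item 1 (SCHEMA, DESIGN) sets the trigger: "If the site investigator diagnoses TB recurrence at any time during Arm 1 follow up", referral to 6 months of standard treatment through the national program follows, and the participant stays in the study for outcome determination. Item 2 gives such participants 65 weeks of follow-up. The new Section 6.3.18 adds symptom calls at weeks 30, 38 and 60. If the investigator is concerned, an in-person visit decides, among other things, "whether the participant should be referred to the local TB program for 6 months of SOC treatment".

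**Outcome A (SAP 3.2.1).** The first route to favorable is "Participants with liquid culture negative status at week 65". All favorable routes carry the condition that "participants must not already have been considered unfavorable, as defined below". There are four unfavorable routes:
- absence of cure, which needs a culture positive for a strain matching the initial isolate and a confirming sample ("A second sputum sample, obtained at least four hours following the first sputum collection");
- death other than violent or accidental;
- a positive culture when last seen;
- "extension of treatment beyond the nominal level (week 13 for Arm 1 and week 26 for Arm 2) due to clinically inadequate response".

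Recurrence with a genotypically proven new strain is unevaluable. The intercurrent events for A in SAP 5.1.2 include no item for retreatment.

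**Outcome B (SAP 3.2.1).** Favorable is the same as in A. The unfavorable list adds any extension other than to make up missed doses, a re-start after at least 30 "consecutive days lost to follow-up", and a change of drug with limited exceptions.

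**Outcome B (SAP 5.1.2).** The table words the re-start gap as time without therapy and lists it under events during therapy. It lists extension under events after adequate completion of therapy.

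**The concern.** A recurrence that leads to a full new course of treatment is a failure of the assigned regimen to produce lasting cure. If the outcome then rests on the week-65 culture, a negative result obtained after, or during, 6 months of rescue therapy is credited to the 3-month regimen. The rescue treatment is the comparator's standard of care, so the contrast between the arms is blurred as well.

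These are the 65-week efficacy outcomes of a trial that closed to accrual because of a high rate of treatment failure and recurrence. SAP version 3.0 was revised to align with LOA #1, so the referral rule was within its scope. The arms are open-label. If the classification stays open, it would be settled with outcome data in hand.

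**Working it through.** The plan states no figure to reproduce. The check traces one case through the definitions and then sizes it.

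**Case.** An Arm 1 participant completes the 13 weeks and stops therapy. The investigator later diagnoses recurrence. No confirmed, genotype-matched positive culture is obtained: the second sample is negative or contaminated, or there is no genotype result. The participant takes 6 months of standard treatment and is culture-negative at week 65.

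**Is the timing possible?** Taking 6 months as 26 weeks, the Arm 2 duration, a course started by week 65 − 26 = 39 is complete by week 65. That is 39 − 13 = 26 weeks after the end of Arm 1 treatment. With a later start, the week-65 sample is taken on therapy. Either way a negative culture is plausible.

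**Trace under A**
- Absence of cure: not met, because the confirmed matched culture is lacking.
- Death: not met.
- Positive when last seen: not met, because the week-65 culture is negative.
- Extension for inadequate response: not met on its ordinary meaning. A new course after an interval off therapy is not an extension, and the unfavorable list of B names extension and re-start separately while A names only extension.
- Unevaluable: not met, because no new strain is proven.
- Result: favorable. In the Kaplan-Meier analysis the participant has no event and no censoring time before week 65.

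**Trace under B**
- Re-start in 3.2.1: not met, because the participant was never lost to follow-up.
- Re-start in 5.1.2: the gap without therapy could be met, but the item sits under events during therapy.
- Extension in 5.1.2: needs no clinical cause and applies after completion, so it could be read to cover a new course.
- Drug change: could be read to apply.
- Result: undetermined.

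**Cases already handled.** A confirmed same-strain recurrence is unfavorable under A and B, and a later negative culture cannot reverse it. A proven new strain is unevaluable and censored. A participant whose last culture is positive is unfavorable, even without confirmation, unless found to be re-infected.

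**Size.** With k such cases among n Arm 1 participants, and ignoring censoring, the Arm 1 proportion shifts by k/n. The planned n is 110 (SAP 2.4). The number at closure is not in the documents, so 70 and 50 are assumed.

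| Arm 1 n | k = 1 | k = 5 |
|---|---|---|
| 110 (planned) | 0.9 points | 4.5 points |
| 70 (assumed) | 1.4 points | 7.1 points |
| 50 (assumed) | 2.0 points | 10.0 points |

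A case in Arm 2 at its planned 55 would move that arm by 1/55 = 1.8 points, so the effect on the difference depends on the counts in both arms.

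**The case against.** **Extension could be read more widely.** The B table in 5.1.2 applies extension after therapy is complete, so the extension clause of A might be read to reach a new course given for clinical failure. That reading is possible, but it is not what A says. A ties extension to treatment beyond the nominal week, and the SAP lists re-start separately elsewhere. Stretching the word would also raise the question of the 13 weeks of rifampicin/isoniazid that LOA #1 adds for Arm 1 participants then on treatment, at least under the cause-free clause of B.

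**Bacteriology will usually be available.** Table 6.1-2 of LOA #1 schedules smear, culture, a molecular assay and drug-susceptibility testing when failure or recurrence is suspected. This stands, and it narrows the gap to unconfirmed cases. It does not close it, because the referral rule speaks of diagnosis and states no culture requirement.

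**Requiring confirmation is deliberate.** In SAP 5.1.3.8 a negative second sample means that no relapse is counted. That is a sound rule for a bacteriological relapse endpoint. It does not settle whether a culture taken after rescue therapy may make a participant favorable on a 65-week outcome.

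**Part of the source is not visible.** Of the protocol, only LOA #1 is available here, and the SAP places coding descriptions in a separate Analysis Implementation Plan. A rule may exist there, so confidence is moderate.

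**A reader might infer that B also scores the case favorable.** The documents do not support that, because three of B's clauses could make it unfavorable.

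**A reader might also infer a known bias toward Arm 1.** Each misclassified case does raise the favorable proportion in its own arm. However, the Arm 1 calls also increase detection of matched positive cultures in that arm, which works the other way, and the Arm 2 referral rule is not shown. The net direction is not established.

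**Conclusion.** The point holds for A as written: an unconfirmed, retreated recurrence that is culture-negative at week 65 is scored favorable and contributes event-free time while on rescue therapy. For B the classification is ambiguous. Neither definition names retreatment for recurrence.

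The size is about 0.9 points of the Arm 1 proportion per case at the planned 110, and more at a smaller n. The number of cases is unknown. A range for the total bias needs assumed rates. For example, 12% to 25% of Arm 1 with failure or recurrence, and 10% to 30% of those retreated without confirmation, gives 0.12 × 0.10 = 1.2 to 0.25 × 0.30 = 7.5 points. None of these is an expected rate in the documents: the 12% is a DSMB review trigger for the lower confidence band, and the rest have no source. The range is illustration only.

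The outcomes are secondary and reported as estimates with intervals, without a formal test, and the 12-week primary efficacy comparison is untouched. This should be corrected, but it does not undermine the trial's main analysis.

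**What to change.** In SAP 3.2.1 A and B, and in both 5.1.2 tables:
- State that a participant who starts TB retreatment for failure or recurrence cannot become favorable on a later culture.
- Count the case as unfavorable (composite strategy) unless genotyping shows a new strain. The event time is the visit at which retreatment was decided.
- Add one sensitivity analysis that censors bacteriologically unconfirmed retreatment at its start.
- Apply the rule to both arms.
- Reconcile the extension and re-start wording of B between 3.2.1 and 5.1.2: lost to follow-up against without therapy, and during therapy against after completion.

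Wording the rule as retreatment for diagnosed failure or recurrence, and not as a wider meaning of extension, keeps it apart from the rifampicin/isoniazid continuation added by LOA #1.

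The cost is SAP wording and one extra analysis. The downside is that some over-diagnosed retreatments in an open-label trial would count as unfavorable; the censoring analysis shows how much that matters. Clinical management does not change.

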##### Unfavorable Outcome

- Absence of cure. A participant will be considered to have absence of bacteriological cure if a sputum sample obtained at or after end of treatment for Arm 1 (week 13), or at or after week 17 for Arm 2 is culture-positive in liquid or solid media for an *Mtb* strain genotypically matched with the initial isolate. A second sputum sample, obtained at least four hours following the first sputum collection (see section 6.2.3 of protocol), is required to confirm absence of bacteriological cure.
- Participants who die from any cause during study treatment or follow-up except from violent or accidental cause (e.g., road traffic accident).

- Participants who had a positive culture for *Mtb* when last seen, whether confirmed by a second sample or not, unless determined to have been re-infected.
- Participants experiencing extension of treatment beyond the nominal level (week 13 for Arm 1 and week 26 for Arm 2) due to clinically inadequate response. These cases should be managed individually in conjunction with and after having notified the A5362 Clinical Management Committee (CMC). Extension of treatment to make up missed doses will not count as unfavorable.

#### Unevaluable Outcome

- Participants lost to follow-up during treatment or post-treatment follow-up with their last culture being negative for *Mtb*.
- Violent or accidental death.
- Participants with recurrent TB due to a new strain of *Mtb* confirmed by conventional molecular genotyping (as defined by MIRU and IS6110 typing).
- Women who become pregnant during their assigned active treatment and stop their assigned treatment.

Favorable, unfavorable, and unevaluable composite outcomes (B) are defined as follows:

#### Favorable Outcome

Same as in outcome measure 3.2.1 A.

#### Unfavorable Outcome

Same as in outcome measure 3.2.1 A, and:

- Participants lost to follow-up during treatment phase of each Arm (i.e., 13 weeks and 26 weeks for Arms 1 and 2, respectively).
- Participants failing to complete treatment (see below for Definitions of Adequate Treatment) and not assessable at the end of the follow-up period.
- Participants receiving any one or more of the following:
  - extension of treatment beyond the nominal level, except to make up missed doses
  - a re-start of treatment following  $\geq 30$  consecutive days lost to follow-up
  - a change in at least one drug in treatment regimen for any reason except re-infection, pregnancy, or temporary drug challenge.

